3.32 Our Ovarian Cancer In Vitro Studies [11]

Our in-vitro data demonstrates that FWGE induces OVCA cell line growth arrest and apoptosis and that it sensitizes OVCA cells to cisplatin-induced cell death. We also have data to suggest that the sensitivity of OVCA cells to FWGE may be determined by a discrete number of molecular signaling pathways.

FWGE induces growth arrest and cell death in ovarian cancer cell lines

We evaluated the effects of FWGE on cell growth arrest in a panel of 12 OVCA cell lines using MTS cell viability assays (Fig 1). Several of these cell lines were paired, mother/daughter, sensitive/resistant lines. Notably, cisplatin-resistance, a surrogate marker of greater chemotherapy-resistance, did not predict FWGE sensitivity. This

suggests the biologic determinants of resistance to chemotherapy agents may differ from those that influence response to FWGE.

for each cell line is shown numerically in ug/ml.

FWGE

potentiates chemotherapy (cisplatin)-induced cell death

To determine if FWGE and the chemotherapy agent cisplatin work synergistically to induce OVCA cell growth arrest, we evaluated 100 and 200 ug/ml FWGE in combination with cisplatin (190, 390, 780, and 1,560nM). Drug activity was evaluated using the combinational index (CI) value determined by the Chou-Talalay isobologram equation where CI<1, CI=1, and CI>1 indicate synergistic, additive, and antagonistic effects. As shown in Figure 2 the majority of FWGE/cisplatin combinations showed greater than additive effects while several combinations were strongly synergistic.

[figure not shown]

Figure 2. Combinational index (CI) values of FWGE and cisplatin drug activity in OVCA cells. CI values of CI<1, CI=1, and CI>1 indicate synergistic, additive, and antagonistic effects.

Expression of genes and signaling pathways that correlate with FWGE sensitivity in OVCA cells

To better understand the mechanisms that underlie FWGE activity in OVCA cells, Affymetrix gene expression data from the 12 cell lines was correlated with FWGE IC50. Using SAM'S Correlation Test (FDR<20%) identified 40 genes associated with FWGE sensitivity in Table 1. In order to place these genes into a relevant biologic

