6.233 RNA extraction and Affymetrix gene expression analysis
A total of 20 fresh frozen primary OVCA tissues (10 FWGE- and 10 placebo-treated) will be used for RNA extraction. Tissues (~30mg) will be submerged in lysis buffer. Tissues are then pulverized in BioPulverizer H tubes (Bio101) using a Mini-Beadbeater (Biospec Products). Tubes are spun briefly to pellet the garnet mixture and reduce foam. The lysates are then transferred to a new 1.5 ml tube using a syringe and 21 gauge needle, followed by passage through the needle 10 times to shear genomic DNA. Total RNA will be collected using the Qiagen RNeasy Mini kit according to the manufacturer's instructions. RNA quality will be checked on an Agilent Bioanalyzer to assess quality of RNA via the 28S:18S ribosomal RNAs.

Microarray analysis: 10 μ g of total RNA will be used to develop the targets for Affymetrix microarray analysis and probes will be prepared according to the manufacturer's instructions. Briefly, biotin-labeled cRNA is produced by in vitro transcription, fragmented, and hybridized to customized Human Affymetrix U133-Plus 2.0 gene chip arrays at 45° C for 16 hours and then washed and stained using the GeneChip Fluidics.

Method of statistical analysis: The expression value will be calculated and normalized using iterative rank-order normalization (IRON) [18]. IRON has been shown to perform better than both MAS5 and RMA and is not model based like RMA. Batch effects will be checked by using PCA; if present, they will be removed using COMBAT [19]. The 54,675 probesets will be screened to remove control probesets, probesets with a small variance, and probesets expressed at low levels.

6.24 Blood will be drawn at the time of surgery and sent for CA125 and a red top tube will be drawn and sent to the laboratory for 2,6, DMBQ testing

6.25 2,6-DMBQ determination

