12.0 STATISTICAL CONSIDERATIONS

12.1 Study Design: This study is a randomized, double-blind, placebo-controlled, trial of the effect of FWGE on women with epithelial ovarian cancer scheduled to undergo surgery. As noted above, we recognize that the sample size in the current study will prohibit definitive statistical conclusions to be drawn on our primary objective (to test the safety and tolerability of FWGE), or our secondary objectives (to compare levels of FWGE active product, CA125 levels, proliferation, and gene expression in OVCAs from subjects receiving FWGE versus placebo). The study is neither designed nor powered to develop statistically significant results, rather, we seek to develop preliminary/pilot data that will enable us to pursue a future large phase II, peer-reviewed grant-funded

trial of adjuvant FWGE in women undergoing therapy for ovarian cancer. Preliminary data developed in the current proposal will support such grant applications.

- 12.2 Primary outcome variable: The principal parameters to be collected, analyzed and reported will be:
- patient and disease characteristics: age, race, co-morbidities, cancer histologic
 type and stage. Optimal versus suboptimal surgical cytoreduction.
 - differences in toxicity
 - differences in quality of life

For each measure, Student's t-test will be used to identify differences between FWGE-versus placebo-treated OVCAs.

- 12.3 Secondary outcome variables for placebo versus FWGE:
- -the presence of 2,6-dimethoxy-p-benzoquinone in the serum
- -the change in the tumor marker CA125,
- -tumor proliferation as measured by Ki-67.

For each measure, Student's t-test will be used to identify differences between FWGEversus placebo-treated OVCAs.

12.4 Secondary outcome variables for genomic changes in ovarian cancer tissue for placebo versus FWGE.

Expression values will be calculated using the robust multi-array average (RMA) algorithm implemented in the Bioconductor (http://www.bioconductor.org) extensions to the R statistical programming environment.

Student's t-test will be used to identify differentially expressed genes in comparisons between FWGE- versus placebo-treated genomic data. Differentially expressed genes will analyzed using GeneGO MetaCore™ software to identify represented biologic pathways.

12.5 Accrual, Sample Size, and Study Duration: The study plan is a one-stage, randomized, double-blind, clinical trial. Patients will be randomized with equal

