probability to receive either FWGE or placebo. The study will accrue 20 patients. It is anticipated that the accrual of this many patients will be achieved in 18 months. Less than 10% of the patients registered are expected to be lost due to follow-up or any other reason, so 20 accruals should allow for 18 evaluable cases.

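### Sections 6.233 and 12.4 name different methods for the array expression values (IRON and RMA), and 12.4 sets no cut-off or FDR for its per-gene t-tests, so the gene list sent to pathway analysis could be mostly false positives

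*Combined protocol and SAP*

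**What the plan says.** Two sections describe how the same arrays are turned into expression values.

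- Section 6.233 (Method of statistical analysis): "The expression value will be calculated and normalized using iterative rank-order normalization (IRON) [18" (the quote stops inside the reference number). It adds: "IRON has been shown to perform better than both MAS5 and RMA and is not model based like RMA".
- Section 12.4: "Expression values will be calculated using the robust multi-array average (RMA) algorithm implemented in the Bioconductor".

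Section 6.233 then describes a batch check and a filter: "The 54,675 probesets will be screened to remove control probesets, probesets with a small variance, and probesets expressed at low levels". The filters have no numeric limits.

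Section 12.4 gives the gene-level analysis: "Student's t-test will be used to identify differentially expressed genes in comparisons between FWGE- versus placebo-treated genomic data". The next step is: "Differentially expressed genes will analyzed using GeneGO MetaCore™ software to identify represented biologic pathways". No significance level, fold-change limit, FDR or other multiplicity rule is stated for the trial arrays.

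The only gene-level rule in the document belongs to the earlier cell-line work in section 3.32: "Using SAM'S Correlation Test (FDR<20%) identified 40 genes associated with FWGE sensitivity in Table 1".

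On numbers, section 6.233 plans 10 FWGE and 10 placebo tissues. Section 12.5 allows for some loss: "so 20 accruals should allow for 18 evaluable cases".

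**The concern.** The two sections cannot be read as successive steps, because each says how the expression values themselves are calculated. Neither method is labelled primary or sensitivity, and the statistical section names the one that the laboratory section argues against. The choice is therefore open, and could be made after results are seen.

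Separately, a t-test yields a p-value per probeset. It does not identify differentially expressed genes until a threshold is fixed. With tens of thousands of tests and about ten arrays per arm, that threshold decides whether the list is mainly signal or mainly noise. The pathway step inherits the list.

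Gene expression is a stated secondary objective (2.222), and the data are meant to support applications for a larger trial. A list dominated by chance findings, or one that depends on the normalisation picked, would carry into the rationale for that trial.

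**Working it through.** **Inputs from the documents.** 54,675 probesets before filtering (6.233); 10 arrays per arm (6.233); 20 patients accrued with equal allocation and under 10% loss (12.5).

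**The plan's own figure.** 20 × (1 − 0.10) = 18 evaluable, or 9 per arm. This reproduces, so both 10 and 9 per arm are used below.

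**Assumptions, because the plan gives none.** Two-sided p<0.05, with 0.01 and 0.001 as a range; 10,000 to 30,000 probesets after filtering; true changes of 1 or 1.5 SD.

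**Step 1: expected false positives if FWGE has no effect.** Count = probesets × α.

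- 10,000 × 0.05 = 500
- 30,000 × 0.05 = 1,500
- 54,675 × 0.05 = 2,734 (upper bound, no filtering)

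These are averages. Correlation between genes leaves the mean unchanged but widens the spread. In 300 simulated trials with 20,000 probesets and ten shared factors carrying 50% of the variance, the mean was 1,027 and the 5th to 95th percentile range was 354 to 2,055. With 30% shared variance the range was 638 to 1,453.

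**Step 2: when is more than half the list false?** Let π be the share of probesets that truly change. False and true selections are equal when (1 − π)α = π × power, so π = α / (α + power). Power comes from the noncentral t with 2n − 2 degrees of freedom and noncentrality d√(n/2). Below this π, most of the list is false.

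| n per arm | α | Power, d=1 | Break-even π | Power, d=1.5 | Break-even π |
|---|---|---|---|---|---|
| 10 | 0.05 | 0.562 | 8.2% | 0.887 | 5.3% |
| 9 | 0.05 | 0.513 | 8.9% | 0.848 | 5.6% |
| 10 | 0.01 | 0.294 | 3.3% | 0.680 | 1.45% |
| 10 | 0.001 | 0.085 | 1.2% | 0.335 | 0.3% |

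Example, first row: 0.05 / (0.05 + 0.562) = 0.082. The break-even share does not depend on how many probesets survive filtering.

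**Step 3: false share at chosen values of π.** False share = (1 − π)α / [(1 − π)α + π × power]. At p<0.05 with 9 to 10 arrays per arm:

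- 1% truly changed: 90–91% false (d=1), 85% (d=1.5)
- 5% truly changed: 63–65%, 52–53%
- 10% truly changed: 45–47%, 34–35%

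**Step 4: what an FDR rule does.** Simulation with 20,000 independent probesets, 2% truly changed, 10 per arm, averages over 100 trials:

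| True change | p<0.05: selected (false) | Benjamini-Hochberg 20%: selected (false) |
|---|---|---|
| 1.5 SD | 1,337 (982) | 222 (44) |
| 1 SD | 1,210 (984) | 13 (4) |

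Repeat runs of the 1 SD case gave 11 to 12 genes with about 3 false, so the last entry is subject to simulation noise. At 5% FDR the 1 SD case yields about 1 gene.

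**The case against.** The best counter-argument is that this is a declared pilot. Sections 2.1, 3.4 and 12.1 each say that the sample size rules out definitive conclusions, and gene expression is named among the affected objectives. No stopping rule or patient decision depends on the gene list. That limits the harm. It does not say which normalisation counts or how a gene is called, and low power makes an uncorrected list worse, because fewer of the selected genes are real.

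Second, the consequence is conditional. The plan does not say that p<0.05 will be used, and the team's one precedent is FDR<20%. At p<0.001 the list is mostly false only if fewer than 0.3% to 1.2% of probesets change. This is right, and it is why the claim is that the list could be mostly false. The absence of a rule needs no assumption.

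Third, the pharmacy holds the allocation key until the study is complete (5.4, Drug Dispensing), so normalisation could be done blind. That reduces the worry about a results-driven choice, but the plan does not commit to doing it in that order.

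Fourth, the FDR comparison in Step 4 uses independent probesets, which flatters the remedy. With 50% shared variance and a 1 SD change, 150 simulated trials at 20% FDR gave a median list of 5 genes. About 21% of trials gave an empty list, and in about 11% more than half the list was false. For 1.5 SD, about 7% of trials exceeded half false. The average false share stayed below 20%, so the control works on average, but a single trial's list can still be poor.

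**Conclusion.** The concern holds. The IRON/RMA conflict is plain on the face of the document and rests on no assumption. So does the missing selection rule: no section gives a threshold for the trial arrays.

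The size is conditional. At an uncorrected p<0.05, the list is mostly false when 5% or fewer of the probesets truly change by 1 to 1.5 SD, and about 500 to 1,500 genes are expected from no effect at all if 10,000 to 30,000 probesets are tested. If 10% or more change, or a much stricter cut-off is used, most of the list may be real. The endpoint is secondary and exploratory, so this is a defect worth correcting rather than one that undermines the trial.

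**What to change.** 1. Name the same single normalisation in 6.233 and 12.4. IRON fits the reasoning already given in 6.233. The other method should appear at most as a labelled sensitivity analysis.
2. In 12.4, declare genes at one fixed Benjamini-Hochberg or SAM FDR, for example the 20% used in 3.32. Send only that list to pathway analysis, with the filtered probesets as background.
3. State the numeric filter limits, so that the number of tests is fixed in advance.

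Optional: a moderated t-test, a rank-based gene-set test (useful if the list is too short for pathway work), and keeping treatment arm in the model if COMBAT is applied.

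The cost is a few sentences and standard software. The real price is a shorter list, which could be empty if effects are near 1 SD. For that reason 20% suits a hypothesis-generating pilot better than 5%.

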GP3	Because of my physical condition, I have trouble meeting the needs of my family	0	1	2	3	4
GP4	I have pain	0	1	2	3	4
GP5	I am bothered by side effects of treatment	0	1	2	3	4
GP6	I feel ill	0	1	2	3	4
GP7	I am forced to spend time in bed	0	1	2	3	4
	SOCIAL/FAMILY WELL-BEING	Not at all	A little bit	Some -what	Quite a bit	Very much
GS1	I feel close to my friends	0	1	2	3	4
GS2	I get emotional support from my family	0	1	2	3	4
GS3	I get support from my friends	0	1	2	3	4
GS4	My family has accepted my illness	0	1	2	3	4

GS5	I am satisfied with family communication about my illness	0	1	2	3	4
GS6	I feel close to my partner (or the person who is my main support)	0	1	2	3	4
Q1	Regardless of your current level of sexual activity, please answer the following question. If you prefer not to answer it, please mark this board and go to the next section.					
GS7	I am satisfied with my sex life	0	1	2	3	4

Please circle or mark one number per line to indicate your response as it applies to the $\underline{past\ 7\ days}$.

	EMOTIONAL WELL-BEING	Not at all	A little bit	Some -what	Quite a bit	Very much
GE1	I feel sad	0	1	2	3	4
GE2	I am satisfied with how I am coping with my illness	0	1	2	3	4
GE3	I am losing hope in the fight against my illness	0	1	2	3	4
GE4	I feel nervous	0	1	2	3	4
GE5	I worry about dying	0	1	2	3	4
GE6	I worry that my condition will get worse	0	1	2	3	4

	FUNCTIONAL WELL-BEING	Not at all	A little bit	Some -what	Quite a bit	Very much
GF1	I am able to work (include work at home)	0	1	2	3	4
GF2	My work (include work at home) is fulfilling	0	1	2	3	4
GF3	I am able to enjoy life	0	1	2	3	4
GF4	I have accepted my illness	0	1	2	3	4
GF5	I am sleeping well	0	1	2	3	4
GF6	I am enjoying the things I usually do for fun	0	1	2	3	4
GF7	I am content with the quality of my life right now	0	1	2	3	4

Please circle or mark one number per line to indicate your response as it applies to the $\underline{past\ 7\ days}$.

	ADDITIONAL CONCERNS	Not at all	A little bit	Some -what	Quite a bit	Very much
01	I have swelling in my stomach area	0	1	2	3	4
C2	I am losing weight	0	1	2	3	4
C3	I have control of my bowels	0	1	2	3	4
02	I have been vomiting	0	1	2	3	4
В5	I am bothered by hair loss	0	1	2	3	4
C6	I have a good appetite	0	1	2	3	4

C 7	I like the appearance of my body	0	1	2	3	4
вмт5	I am able to get around by myself	0	1	2	3	4
В9	I am able to feel like a woman	0	1	2	3	4
03	I have cramps in my stomach area	0	1	2	3	4
BL4	I am interested in sex	0	1	2	3	4
ВМТ7	I have concerns about my ability to have children	0	1	2	3	4

MCC 17883

Protocol Revision 06/09/2017 – Summary of Changes

• Changed minimum timeline needed for FWGE and surgery
